10.9. Appendix 9: Tuberculosis Testing

This table describes recommendations for performing and interpreting TB tests. It also provides recommendations on TB retesting.

TB test type	How to perform the test	How to interpret the test	When to retest
CCI	Ensure that specimen handling,	Results are provided by the	The investigator may
	transport, timing, and	laboratory assaying the test.	discuss retesting with the
	laboratory procedures meet all		sponsor's designated
M tuberculosis	requirements per package		medical monitor if
	insert.		• the investigator suspects
			a false-positive
			CCI Gold
			test result in a participant
			with no increased risk of
			TB infection during
			lifetime, and
			• there is no evidence of
			prior or current TB on
			physical examination
			and/or on CXR
			interpreted by radiologist
			and/or pulmonologist
			(investigator assessment
			by history and physical
			examination, and with
			documented CXR
			report).

Abbreviation: CXR = chest X-ray.

10.10. Appendix 10: Permitted Concomitant Medications/Therapies

Drug Class (examples) –	Screening and Washout	Т	reatment			
Comments by Study Period	I	II	III			
Oral 5-ASAs (mesalamine, balsalazide, olsalazine) and sulfasalazine for UC • if participant is on a stable prescribed dose weeks before screening endoscopy	If continuing stable screening prescribed dose must remain Visit 6 (Week)	May continue with stable dose encouraged				
Oral corticosteroids for UC • prednisone comg/day or equivalent, or • extended-release budesonide tablets (budesonide MMX) mg/day, or • beclomethasone dipropionate mg/day (gastro-resistant, prolonged-release tablet) • if participant on stable prescribed dose weeks before screening endoscopy	If continuing stable screening prescribed dose must remain s Visit 6 (Week)		Tapering of dose may begin at Visit 6 (Week). See Section 6.8.1			
Corticosteroids for non-UC indications	Stable doses encouraged continued use/regimen to treat adrenal insufficiency locally administered use, e.g., inhaled, intranasal, intraarticular, topical, and single doses, oral or IV, as premedication for mirikizumab administration in participants with prior mirikizumab/other biologic administration reactions					
Oral AZA, 6-MP, MTX for UC indication • if participant on stable prescribed dose weeks before screening endoscopy Topical JAK inhibitors and calcineurin inhibitors	If continuing stable screening remain stable throughout the needed due to AEs related to As needed	study unless n	nodifications are			
Antidiarrheals (loperamide, diphenoxylate with atropine)	Stable doses encouraged					
Low-dose or baby aspirin (CCI mg) Non-live vaccines (killed, inactivated, subunit, or RNA-based)	Daily use of a stable dose for If a non-live vaccine is neede intervention not be administe vaccination	d, it is recomn	nended that study			
Complementary alternative medicine for non- UC indications (dietary or herbal supplements, vitamins, probiotics)	Stable regimen and doses enc Other nonprescription medici permitted following discussion	nes in this cate				

Abbreviations: 5-ASA = 5-aminosalicylic acid; 6-MP = 6-mercaptopurine; AE = adverse event; AZA = azathioprine; IV = intravenous; JAK = Janus kinase; MMX = Multi matrix colonic delivery technology; MTX = methotrexate; UC = ulcerative colitis.

10.11. Appendix 11: Prohibited Medications

This section outlines medications that are prohibited during the treatment phase of the study and during washout periods prior to the screening endoscopy, if applicable. Use of the medications listed in this appendix is allowed at the discretion of the investigator after a participant discontinues study intervention and completes the ED visit.

Drug Class (examples) –	Screening and Washout	Tre	atment
Comments by Study Period			
	I	II	III
Biologics, JAK inhibitors, Immunomodulators			
Anti-TNF antibodies	DC CCI prior to screening	Pro	hibited
(adalimumab, golimumab, infliximab)	endoscopy		
CCI	DC CC prior to screening	Pro	hibited
	endoscopy. See Section 5.2.		
Anti-integrin antibodies	DC CCI prior to screening	Pro	hibited
(vedolizumab)	endoscopy		
JAK inhibitors, oral	DC cc prior to screening	Pro	hibited
(tofacitinib, upadacitinib)	endoscopy		
CCI	DC CC prior to screening	Pro	hibited
	endoscopy		
Immunomodulators for UC: oral AZA, 6-MP,	Initiation or increase above	the stable dose	at screening is
MTX	-	uring the study	
Immunomodulatory medications, oral or IV:	DC CCI prior to screening	Pro	hibited
cyclosporine, mycophenolate mofetil,	endoscopy		
thalidomide, tacrolimus.			
Other immunomodulatory medications should			
be discussed with medical monitor prior to use			
Corticosteroids			
Rectally administered corticosteroids,	DC CCI prior to screening	Pro	hibited
enemas or suppositories	endoscopy		
Oral corticosteroids for UC	Initiation or increase above the		se at screening is
	 	uring the study	
Oral budesonide standard formulation	DC CCI prior to screening	Pro	hibited
- Note: this is not budesonide MMX	endoscopy		
IV corticosteroids for UC	DC CCI prior to screening		orticosteroids
	endoscopy	•	hibited
Systemic corticosteroids for non-UC indication,	DC CCI prior to screening	Pro	hibited
oral or IV. Allowed exceptions: See Section	endoscopy		
10.10.			

Drug Class (examples) –	Screening and Washout	Treatment			
Comments by Study Period	I	II	III		
Other					
Rectally administered 5-ASA therapies - enemas, suppositories	DC CC prior to screening endoscopy	Pro	hibited		
Agents depleting B or T cells (alemtuzumab, rituximab, visilizumab)	DC col prior to screening endoscopy	Pro	hibited		
Any investigational therapy, biologic or non-biologic	DC or half-lives, whichever is longer, prior to screening endoscopy	Pro	hibited		
Rectally administered investigational preparations for UC (arsenic)	DC prior to screening endoscopy	Pro	hibited		
Interferon therapy	DC prior to screening endoscopy	Pro	hibited		
Leukocyte apheresis, leukapheresis (Adacolumn)	DC prior to screening endoscopy	Pro	hibited		
BCG vaccination	Not CCI prior to Visit 2		so CCI after last mirikizumab		
Live or attenuated vaccines (for measles, mumps, rubella, or varicella). See Section 6.8.3.	Not prior to Visit 2		so CCI after last mirikizumab		
Nonprescription complementary alternative medicines for UC indication (dietary/herbal supplements, vitamins, probiotics)	Prohibited May consult wi	during study. th medical mon	itor		
Medicinal and recreational marijuana	DC or prior to screening endoscopy	Pro	hibited		

Abbreviations: 5-ASA = 5-aminosalicylic acid; 6-MP = 6-mercaptopurine; AZA = azathioprine; BCG = Bacillus Calmette-Guerin; DC = discontinue; IL= interleukin; IV = intravenous; JAK = Janus kinase; M = month; MMX = multi matrix colonic delivery technology; MTX = methotrexate; S1P = Sphingosine-1-phosphate; TNF = tumor necrosis factor; UC = ulcerative colitis; W = weeks.

10.12. Appendix 12: Optional Continued Access Period

10.12.1. Overview

The Continued Access Period is offered to sites with eligible study participants who complete AMBZ Study Periods I to III.

The duration of the Continued Access Period will differ by participant and country.

Efficacy data will not be collected during the Continued Access Period. Participants will continue to be followed for safety throughout their participation in this Continued Access Period.

Study activities and procedures described in this appendix are in addition to the requirements of the main AMBZ protocol, unless otherwise specified. Some information from the main AMBZ protocol is repeated for clarity.

^a Participants who are eligible for Continued Access should move directly from Visit 10 to Visit 501, on the same day, if possible. Visit 801 should not be performed.

10.12.3. Schedule of Activities for Continued Access Period

Throughout this appendix, "self-administration" refers to CCI of mirikizumab by the participant or caregiver.

All visits

Self-administration of mirikizumab mg ccl is required at all visits, regardless if the visit is onsite, or telehealth or remote. All activities should be completed prior to self-administration of mirikizumab, unless otherwise stated below.

Continued Access Treatment (Visit 501 to last dosing visit)

Visit 501 activities should occur on the same day as Visit 10 of Study Period III.

Complete all Visit 10 activities before starting Visit 501 activities and dosing.

If Visit 10 and Visit 501 do not occur on same day, Visit 501 activities may need to be repeated, as detailed in the continued access period SoA.

If Visit 10 and Visit 501 occur more than 2 weeks apart, the following laboratory tests must be repeated: hematology, clinical chemistry, and HBV DNA.

Extended continued access visits (ECAV)

After Visit 507 (Week CO), ECAV continue until criteria for the final visit occurs.

Visits ECAVa, ECAVb, and ECAVc occur every weeks.

Visit ECAVa and ECAVb represent telehealth or remote visits that occur every weeks, and follow an onsite visit.

Visit ECAVc represents the quarterly onsite visit.

Visit numbers will be registered sequentially after Visit 507. This table provides an example of the visit structure that will continue until the final visit.

Visit Number	Visit ID	Weeks from Visit 2
507	507	
ECAVa	508	
ECAVb	509	
ECAVc	510	
ECAVa	511	
ECAVb	512	
ECAVc	513	

Discontinuation (DC) visit

All participants who discontinue mirikizumab treatment after Visit 501 should complete this DC Visit.

Continued Access Period follow-up (weeks)

Visit 901

All participants will complete this visit following their DC visit or at the end of their participation in the Continued Access Period of the study.

Visit 901 may be performed onsite when onsite activities are required or at investigator's discretion.

Unscheduled visits

Unscheduled visits may occur as needed, on any day without regard to visit interval. Required activities are indicated in the SoA. Additional procedures may be performed at the investigator's discretion.

	AMBZ Continued Access Period												Comments	
Visit number	501	502	503	504	505	506	507	ECA Va	ECA Vb	ECA Vc	DC	UV	V901	ECAV = extended continued access visit DC = discontinuation visit
CC														CCI
Visit conduct	O	Т	Т	0	Т	Т	0	Т	Т	0	0	0	Т	O = onsite; T = telehealth/remote visit \$\pm\$ = If Visit 10 and Visit 501 do not occur on same day, these activities must be repeated \$\pm\$ = If Visit 10 and Visit 501 occur >2 weeks apart, these laboratory tests must be repeated
Informed consent	X													ICF must be signed before any continued access-specific activities are performed.
Inclusion and exclusion criteria	X													Review and confirm specific inclusion and exclusion criteria before V501 activities and dosing.
Substance use, including alcohol, caffeine, tobacco, nicotine											X			
Concomitant medications	XĻ	X	X	X	X	X	X	X	X	X	X	X	X	
Adverse events (AEs)	XĻ	X	X	X	X	X	X	X	X	X	X	X	X	See Sections 8.3.1 and 8.3.3.
Physical evaluation	on								_					
Weight	X↓			X			X			X	X			
Vital signs	X↓			X			X			X	X			See Section 8.2.2.
Symptom- directed physical assessment	X↓			X			X			X	X			See Section 8.2.1.
Evaluate for EIMs	XĻ			X			X			X	X			See Section 8.2.1.

Tuberculosis														TB risk factors; symptoms of active TB. See
(TB) evaluation	X↓			X			X			X	X			Section 8.2.7.
	Participant education													
Self- administration retraining						X								Complete at the investigator's discretion. See Section 10.12.6.
Laboratory tests														
Hematology	X↓↓			X			X			X	X	Χŧ	X‡	† Optional per investigator discretion.
Clinical Chemistry	X↓↓			X			X			X	X	Χŧ	X‡	Optional per investigator discretion.
Urine pregnancy (local)	XĻ	X	X	X	X	X	X	X	X	X	X		X	Must be performed, with negative result available, prior to dosing at each visit, for WOCBP.
Follicle stimulating hormone (FSH)						X								Optional, perform as needed to confirm postmenopausal status in female participants. See Section 8.2.5.
HBV DNA	X			X			X			X	X			Only required for participants with positive HBV serology at screening. See Section 8.2.8.
Pharmacokinetic (PK) samples Immunogenicity (ADA) samples		Collec			_	oles in t		of a potent	tial systemeaction.	mic drug				Collect PK and ADA samples as detailed in Section 10.2.
Endoscopy Proce	dures											1		
Endoscopy		No	t requir	ed, ma	y perfo	rm per	investiga	tor's discr	retion.					If performed, conduct local read.
Registration and	dosing		•			•					J.	1		
Register visit with IWRS	X	X	X	X	X	X	X	X	X	X	X		X	
Dispense mirikizumab via IWRS	X			X			X			X				
Self-administer mirikizumab	X	X	X	X	X	X	X	X	X	X				

Provide self- administration materials for remote dosing	X		X		X		X		Materials include mirikizumab; SDALs; and ancillary supplies, including urine pregnancy tests for WOCBP.
Review SDALs									See Section 10.12.6.
and mirikizumab	X		X		X		X		
cartons									

ICF = Informed consent form; IWRS = interactive web response system; SDAL = Study Drug Administration Log; V= Visit; WOCBP = women of childbearing potential

10.12.4. Overall Design

Transition of participants from the main study to continued access

A participant will

• complete all AMBZ Visit 10 activities, including the Visit 10 study endoscopy with biopsies, and

- complete Visit 501 of the Continued Access Period.
 - If a potentially eligible participant does not meet all inclusion and exclusion criteria at Visit 501, that participant should enter the posttreatment follow-up period of the main study protocol and complete Visit 801 as indicated in Section 1.3.
 - If a potentially eligible participant meets all inclusion and exclusion criteria at Visit 501, that participant should continue visits and procedures according to the SoA in Section 10.12.3.

10.12.5. Study Population

The inclusion and exclusion criteria in this section are specific to this Continued Access Appendix.

The inclusion and exclusion criteria stated in Section 5 do not apply to participant eligibility for continued access, unless that criterion is re-stated below.

10.12.5.1. Inclusion Criteria

Participants are eligible to enter the Continued Access Period only if all the following criteria apply.

Informed consent

52. Are capable of giving signed informed consent to take part in the continued access period, prior to any procedures specific to Continued Access Period being completed.

Participant and disease characteristics

- 53. Have completed AMBZ Study Periods I to III, including
 - all Visit 10 activities, including the endoscopy with biopsies
 - administration of at least CCI mg mirikizumab doses, without early termination of mirikizumab in Study Period III
 - self-administration training, or demonstrate willingness and ability to complete training and/or retraining, and
 - in the opinion of the investigator, would continue to derive benefit from treatment with mirikizumab
- 54. Have the ability to complete Visit 501, including the first dose of mirikizumab of the Continued Access Period, on the same day as Visit 10, or within approximately 4 weeks after Visit 10.

• It is strongly recommended that no more than weeks occur between Visit 9 of Period III and Visit 501 of the Continued Access Period. Participants requiring a longer duration for entry into the Continued Access Period, but not to exceed approximately weeks, must be discussed on an individual basis with the medical monitor.

- 55. Are up-to-date with surveillance colonoscopy requirement per Section 8.1.5.2, with documented negative results for colorectal dysplasia and cancer. If needed, a colonoscopy with biopsies should be the endoscopic procedure performed at Visit 10 (Week).
- 56. Are willing and able to complete the scheduled visit activities for the Continued Access Period, including self-administration of mirikizumab (by participant or caregiver). Also, in the opinion of the investigator, are able to reliably perform remote, self-administration procedures and related required documentation.

Sex and contraceptive/barrier requirements

57. Agree to adhere to the contraception requirements specified in Section 10.4.

10.12.5.2. Exclusion Criteria

Participants are excluded from the Continued Access Period if any of the following criteria apply:

Gastrointestinal exclusion criteria

- 58. Have been diagnosed with CD, inflammatory bowel disease-unclassified, formerly known as indeterminate colitis.
- 59. Have had bowel resection or other surgery for the treatment of UC or are likely to require surgery for the treatment of UC during the Continued Access Period.
- 60. Have had evidence of toxic megacolon, intra-abdominal abscess, or stricture or stenosis within the small bowel or colon prior to Visit 501 of the Continued Access Period.
- 61. Have evidence of cancer of the gastrointestinal tract prior to Visit 501 of the Continued Access Period.
- 62. Have evidence of current sporadic adenoma without dysplasia (adenomatous polyps occurring proximal to known areas of colitis), that has not been removed. If completely removed prior to Visit 501, this exclusion criterion would no longer apply.

 Note: Once removed, the participant may be eligible for the Continued Access Period, after confirming no dysplasia or malignancy on local histology report; and the maximum roll-over period to enter the Continued Access Period has not been exceeded.
- 63. Have current evidence of colonic dysplasia prior to Visit 501, including
 - polypoid or non-polypoid lesion(s) of colonic mucosa in an area which is endoscopically visible or invisible, and
 - histopathology report of "indefinite for dysplasia," low-grade dysplasia, or high-grade dysplasia.

Infectious disease exclusion criteria

64. Have been diagnosed with a clinically important infection including, but not limited to, hepatitis B, hepatitis C, HIV/AIDS, and active tuberculosis (TB) prior to Visit 501 of the Continued Access Period.

- 65. Have detectable hepatitis B virus (HBV) DNA detected at any time prior to Visit 501 of the Continued Access Period.
- 66. Have been diagnosed with LTBI prior to Visit 501 of the Continued Access Period and are not willing to comply with completing TB treatment as appropriate.
- 67. Intend to receive a Bacillus Calmette-Guerin (BCG) vaccination or live attenuated vaccine(s) during the Continued Access Period.

Other exclusion criteria

- 68. Have been diagnosed with a condition, underwent a surgical procedure, received prohibited treatment, or experienced a laboratory abnormality that met criteria for permanent discontinuation from mirikizumab treatment prior to Visit 501 of the Continued Access Period. See Section 7.1.
- 69. Currently meet temporary discontinuation of study intervention criteria (see Section 7.1.4). Note: Once resolution of the condition or appropriate treatment is met, the participant may be eligible for the Continued Access Period if the maximum roll-over period to enter the Continued Access Period has not been exceeded.
- 70. Have initiated a new prohibited medication (see Section 10.11) prior to Visit 501 of the Continued Access Period.
- 71. Have had evidence of alcohol dependence or illicit drug abuse prior to Visit 501 of the Continued Access Period.
- 72. Have had the presence of a hepatic or hematologic laboratory abnormality prior to Visit 501 of the Continued Access Period, that would require permanent discontinuation from mirikizumab treatment. See Section 7.1.
- 73. Have an underlying disease, or surgical, physical, or medical condition that, in the opinion of the investigator, would potentially affect participant safety within the continued access period.
- 74. Have a known systemic hypersensitivity to any component of mirikizumab, or have experienced an acute systemic hypersensitivity event with previous mirikizumab treatment administration, that precludes mirikizumab treatment.
- 75. Are pregnant or planning pregnancy (females only) while enrolled in the continued access period, or within weeks after receiving the last dose of mirikizumab.
- 76. Became part of the investigator site personnel directly affiliated with this study or their immediate families prior to Visit 501 of the Continued Access Period.
- 77. Became a Lilly employee or an employee of third-party organizations involved with the study prior to Visit 501 of the Continued Access Period.
- 78. Have enrolled in any other clinical study involving an investigational product or any other type of medical research judged not to be scientifically or medically compatible with this study.

79. Are unsuitable for inclusion in the continued access period in the opinion of the investigator or sponsor for any reason that may compromise the subject's safety.

10.12.6. Study Intervention

All participants enrolled in the Continued Access Period will self-administer mg mirikizumab CCl

Administration of mirikizumab should always be done after completion of all other visit activities, as specified in SoA (Section 10.12.3).

At all telehealth or remote dosing visits, self-administration of mirikizumab should be performed immediately following completion of the telephone-portion of the visit.

If self-administration is not possible at a visit, the study site staff may administer the dose at the study site and provide source documentation for the reason. If self-administration is not possible for repeated visits, study site should contact the medical monitor.

Reporting requirements

All required self-administration dosing information must be documented on the relevant SDALs for each visit. Deviations from the prescribed dosing regimen should be documented by the participant on the SDAL and recorded by site staff in the CRF.

Following review of the completed SDALs, and returned mirikizumab CCI cartons, including any unused CCI is, if the site staff identifies any deviations from correct procedures, incomplete doses administered, PCs, and/or CCI concerns from participant, appropriate corrective actions, including retraining, should be completed.

Treatment compliance

Compliance with study intervention will be assessed at each visit. Compliance will be assessed by direct questioning, counting unused syringes, review of SDALs, and documented in the source documents.

If a participant is noncompliant with self-administration procedures, the investigator should determine the reason for noncompliance and educate or manage the participant as appropriate to improve compliance.

If, in consultation with the medical monitor, the noncompliance is deemed to be significant such that it affects the safety of the participant or the evaluation of the safety data during the Continued Access Period, the participant should be discontinued from the Continued Access Period.

10.12.7. Discontinuation of Study Intervention and Participant Discontinuation from the Study

In addition to the study intervention discontinuation requirements in Section 7.1, the following also apply to the continued access period:

Following discontinuation from mirikizumab during the continued access period, the participant should complete both the discontinuation visit and Visit 901, as indicated in the Continued Access Period SoA (Section 10.12.3).

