6.8.2. Prohibited Medications

Administration of prohibited medications for the treatment of UC, approved or investigational, constitutes treatment failure. Use of such medications should not be withheld if, in the opinion of the investigator, failure to prescribe them would compromise participant safety. Participants who require a prohibited medication to treat their UC must be discontinued from study intervention, complete an ED visit, and a posttreatment follow-up visit.

A participant who requires a prohibited medication for a non-UC indication should be discussed with the medical monitor.

Section 10.11 provides the list of prohibited medications and details.

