7.1. Discontinuation of Study Intervention

When necessary, a participant may be permanently discontinued from mirikizumab. If so, the participant will discontinue mirikizumab and will remain in the study to complete procedures for an ED visit, if applicable, and posttreatment follow-up, as shown in the SoA.

A participant should be permanently discontinued from study intervention (mirikizumab) if

the participant becomes pregnant during the study

in the opinion of the investigator, the participant should permanently discontinue the study intervention for safety reasons

the participant has a lack of clinical benefit or disease worsening and

o requires treatment with medication(s) at doses higher than those specified in Sections 10.10 and 10.11.

or

o requires treatment with prohibited medications specified in Section 10.11.

the participant undergoes surgery for active UC

the participant has a systemic hypersensitivity reaction (Section 7.1.3)

the participant has a diagnosis of the following during the study:

- malignancy (except for successfully treated basal or squamous cell skin carcinoma),
 or
- intestinal dysplasia

the participant develops HIV infection.

the participant develops active TB or has untreated LTBI (Section 8.2.7).

HBV or HCV: the participant tests positive for HBV DNA (see Section 8.2.8.1) or tests positive for HCV RNA (Section 8.2.8.2)

Note: The HBV DNA result is to be confirmed if initial test result is positive but below the level of quantification (Section 8.2.8.1).

Prior to discontinuation of any immunomodulatory and/or immunosuppressive therapy due to hepatitis, including study intervention, it is recommended that the participant is to be referred to, evaluated, and managed by a specialist physician with expertise in evaluation and management of viral hepatitis.

The timing of discontinuation from study intervention relative to the initiation of any antiviral treatment for hepatitis is to be based on the recommendation of the consulting specialist physician, in conjunction with the investigator, and aligned with medical guidelines and standard of care.

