10.12.9. Permitted Concomitant Medications/Therapies during Continued Access

Note: At the discretion of the investigator, any permitted concomitant medication may have the dose modified, be discontinued, or be re-started during the Continued Access Period. If there are any questions on these permitted medications, please contact the medical monitor.

	-
Drug Class (examples)	Comments
Oral corticosteroids or oral budesonide (standard or extended-release formulation [budesonide MMX]) for UC • prednisone mg/day or equivalent • budesonide MMX mg/day, or • beclomethasone dipropionate mg/day (gastro-resistant prolonged-release tablet)	Short courses of corticosteroids, including budesonide, are permitted with tapering to begin as soon as clinically feasible, with a goal of discontinuing within 3 months. Participants who require increasing doses and repeated courses or are intolerant to tapering of corticosteroids should be considered for treatment discontinuation and termination from the Continued Access Period
Corticosteroids for non-UC indications	Permitted as follows:
	continued use to treat adrenal insufficiency
	locally administered use, e.g., inhaled, intranasal, intraarticular, and topical
	single doses (oral or IV) corticosteroids as premedication for miri self-administered CCI and
	limited use for acute conditions per investigator discretion
Rectally administered corticosteroids (enemas or suppositories)	Permitted with the goal of tapering as soon as clinically feasible or discontinuing within 3 months. Participants who require continuous use of steroid enemas or suppositories or are intolerant to tapering should be considered for treatment discontinuation and early termination from the Continued Access Period
Immunomodulators for UC	Permitted
(oral AZA, 6-MP, or methotrexate)	
Oral 5-ASAs (mesalamine, balsalazide,	Permitted
olsalazine) and sulfasalazine for UC	
Rectally administered 5-ASAs	Permitted
(enemas or suppositories)	Da
Topical JAK inhibitors and calcineurin inhibitors	Permitted
Antidiarrheals	Permitted
(loperamide, diphenoxylate with atropine)	1 omittee
Low-dose or baby aspirin (75 to 162.5 mg)	Daily use for cardiovascular prophylaxis permitted
Non-live vaccines	Permitted
(killed, inactivated, subunit, or RNA-based)	
Complementary alternative medicine for UC and non-UC indications	Permitted

(dietary/herbal supplements, vitamins,	
probiotics)	

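### Continued access permits rectal corticosteroids, rectal 5-ASA and AZA/6-MP/MTX, but protocol Section 10.12.7 imports a stopping rule tied to a list that prohibits or restricts them

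*Protocol*

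**What the plan says.** Section 10.12.7 of the protocol covers stopping treatment in the Continued Access Period (CAP). Its lead-in is "In addition to the study intervention discontinuation requirements in Section 7.1, the following also apply to the continued access period". Section 7.1 therefore applies in the CAP, and further criteria are added to it.

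Section 7.1 begins "A participant should be permanently discontinued from study intervention (mirikizumab) if". One of its conditions is "the participant has a lack of clinical benefit or disease worsening and", completed by either of two triggers: a need for doses above those in Sections 10.10 and 10.11, or that the participant "requires treatment with prohibited medications specified in Section 10.11".

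Section 10.11 prohibits enemas and suppositories containing corticosteroids. It also prohibits "Rectally administered 5-ASA therapies - enemas, suppositories". For AZA, 6-MP and methotrexate, it prohibits starting them or going above the stable screening dose.

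Section 10.12.9 lists what is allowed in the CAP. Rectal corticosteroids are "Permitted with the goal of tapering as soon as clinically feasible or discontinuing within 3 months"; stopping mirikizumab is only to be considered, and only if use becomes continuous or the participant cannot taper. Rectal 5-ASA and oral AZA, 6-MP or methotrexate for UC are permitted without conditions. A note lets the investigator change the dose of any permitted drug, stop it or restart it.

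Section 10.12.10 is a separate prohibited list for the CAP. None of these three classes appears on it.

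**The concern.** The CAP has its own lists of permitted and prohibited drugs, but the stopping rule that it takes from the main protocol still points to the main-study list. Where the two lists differ, the same prescription is allowed by one section and grounds for permanent discontinuation under another.

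A flare during continued access is foreseeable, and Section 10.12.9 provides for short-term treatment of one. Whether a participant then keeps mirikizumab would depend on which section the site follows. The SAP plans a CAP safety analysis covering disposition, adverse events, vital signs and laboratory data (Section 4.1.3), reports reasons for stopping treatment (Section 4.2), and closes the CAP at the treatment discontinuation visit (Section 1.2). Different site readings would therefore alter both the disposition table and the length of follow-up.

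**Working it through.** No arithmetic applies. The check follows the cross-references and compares the lists row by row.

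**Step 1: the chain.** Section 10.12.7 brings in Section 7.1. Section 7.1 names Section 10.11 in its prohibited-drug trigger, and Sections 10.10 and 10.11 in its dose trigger. Neither Section 7.1 nor the visible text of Section 10.12.7 mentions Section 10.12.10.

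**Step 2: the rows.**

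| Class | 10.11 (main study) | 10.12.9 (CAP permitted) | 10.12.10 (CAP prohibited) |
|---|---|---|---|
| Rectal corticosteroids | Prohibited | Permitted; stopping mirikizumab considered only for continuous use or failure to taper | Not listed |
| Rectal 5-ASA | Prohibited | Permitted | Not listed |
| Oral AZA, 6-MP, methotrexate for UC | Starting, or exceeding the stable screening dose, prohibited | Permitted; dose change and restart allowed | Not listed |

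The first two rows conflict explicitly. In the third, dose increases conflict through the note on dose changes. That a first-ever start is allowed is an inference from an unqualified permission.

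**Step 3: one case traced through.** A CAP participant's colitis worsens and a first course of rectal corticosteroid is needed.

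- Under Section 10.12.9 the course is allowed. Stopping mirikizumab is not raised unless use becomes continuous or tapering fails.
- Under Section 7.1, reached through Section 10.12.7, both parts of the trigger are met: disease worsening, and need for a drug on the Section 10.11 list. The participant should permanently stop.

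The two routes give different outcomes from the same facts. Section 7.1 needs both parts, so use of such a drug without worsening or lack of benefit does not trigger it.

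**Step 4: does the visible text break the chain?**

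- Section 10.12.1 says: "Study activities and procedures described in this appendix are in addition to the requirements of the main AMBZ protocol, unless otherwise specified". That leaves main-protocol rules in force unless the appendix displaces them.
- Where the appendix means to displace a main-protocol rule, it can say so plainly: Section 10.12.5 switches off the Section 5 entry criteria unless they are restated. Section 10.12.7 does the reverse for Section 7.1.
- The appendix still uses Section 10.11 itself, in CAP exclusion criterion 70, so a site cannot assume that list is irrelevant once the main study ends.
- Section 6.8.2 points the same way in the main protocol: "Participants who require a prohibited medication to treat their UC must be discontinued from study intervention". Section 10.12.7 does not cite it, so it supports the reading without being needed for it.

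Nothing visible replaces the reference to Section 10.11.

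**The case against.** The strongest reply is that the two lists belong to different periods. Section 10.11 describes itself as covering the treatment phase, and its columns stop at Period III. It frees its drugs for use after the early discontinuation visit, which exists only for those who stop before Visit 10. Section 10.12.10 gives the CAP its own list, tied to the CAP discontinuation visit. Criterion 70 applies Section 10.11 only to drugs started before Visit 501. On this view Sections 10.12.9 and 10.12.10 are the exception that Section 10.12.1 allows for. The milder rule for rectal corticosteroids would have little purpose if first use for worsening colitis already meant stopping. A site would naturally consult the table written for continued access, and that table sends questions to the medical monitor.

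This is probably the intent, and it keeps the point modest. It does not remove it, because the text that governs stopping still names Section 10.11.

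A second reply stands as a limit. The Section 10.12.7 lead-in ends in a colon, and the criteria after it are not visible. Since they are introduced as additions, they would not be expected to cancel a Section 7.1 trigger, but this cannot be confirmed.

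A reader might also infer that five or more classes are in conflict, adding standard-formulation budesonide and complementary medicines for UC. The documents support that less well. Standard budesonide sits inside the oral corticosteroid row of Section 10.12.9, which belongs to a related mismatch with Section 10.12.10. For complementary medicines, Section 10.11 itself offers consultation with the medical monitor.

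**Conclusion.** The inconsistency is real and should be corrected. It is explicit for rectal corticosteroids and rectal 5-ASA. For AZA, 6-MP and methotrexate it is sound for dose increases and inferred for new starts. It rests on two assumptions: that the unseen criteria in Section 10.12.7 do not redirect the Section 7.1 triggers to the CAP lists, and that the participant has worsening disease or lack of benefit.

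Its reach is limited to who stays on mirikizumab in the CAP, the CAP disposition summary and CAP safety follow-up. A reader might infer a threat to the study's efficacy results. The documents do not support that: no efficacy data are collected in the CAP (protocol Section 10.12.1), and the main analysis stops at the end of Period III (SAP Section 4.1.3). Nor do they support a percentage of participants affected, since they give no rate of flare or of use of these drugs. It would also go too far to say that one reading always stops treatment, because Section 7.1 is worded as a recommendation with two conditions.

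**What to change.** Reconcile Sections 7.1, 10.11, 10.12.7, 10.12.9 and 10.12.10. The simplest vehicle is a sentence in Section 10.12.7 stating which medication lists the two Section 7.1 triggers (doses above the stated limits, and prohibited drugs) refer to during continued access, so that each agent has one status and one consequence. Deal in the same edit with the mismatch on oral corticosteroids for UC, where Section 10.12.9 allows short courses and Section 10.12.10 prohibits initiation or an increase above the screening dose. Which rule stands is for the sponsor's clinical team.

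The cost is a short text change at the next amendment and a clarification to sites. No new data collection or change to the analysis is needed.
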